8.1.1 HCP recruitment

HCPs include both physicians and nurses.

- A) Physicians: A target list of physicians known to be prescribing Fabrazyme home infusion will be provided by the MAH and used for recruitment. Potentially eligible physicians will be approached via telephone or email with information about this study. The method of contacting physicians is dependent on contact details provided in the target list.
- B) Nurses: Based on information provided by the MAH, Nurses play an important role in providing in person medical supervision and education to patients receiving Fabrazyme home infusion in the UK, France, Italy and Finland. Therefore nurses will be included in the HCP sample in these markets. To recruit nurses we will use a mix of both targeted recruitment and via physician referral; for targeted recruitment the MAH will provide a list of external home care provider companies with contact details per market. Potentially eligible nurses will be contacted via telephone or email with information about this study. The method of contacting nurses is dependent on contact details obtained via the physicians or home care providers.

To increase participation in the survey all HCPs on the target lists will be sent a letter of endorsement from the MAH and MAH representative that provides information to validate the regulatory requirement associated with the reason for the survey. Interested HCPs will be asked screening questions to check eligibility for the survey.

Inclusion/exclusion criteria:

- Involved in the treatment of at least 1 patient with Fabry disease in the last 12 months
- Have prescribed Fabrazyme for home infusion and/or monitor, oversee the management, and/or provide in person medical supervision of patients on Fabrazyme home infusion in the last 12 months
- Not a current or ex-employee of Sanofi

If the criteria are met, HCPs are asked to provide consent to participate in the study. Once consent has been provided HCPs is provided with a link to access and complete the main survey.

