8.7 DATA ANALYSIS

The analysis will be cross-sectional and descriptive. Categorical data will be summarized by counts and percentages. Continuous data will be summarized using number, median, minimum and maximum values. Missing data will be noted for each variable.

A **positive outcome** reported across key pre-defined questions for each of these objectives would support the effectiveness of the educational material. For this assessment, a positive outcome is defined as at >70% of the survey participants providing a ‘correct’ response (specific questions and responses are outlined in Tables [Table 8](#) and [Table 9](#)). The 70% cut point is based on previous experience from other surveys evaluating the effectiveness of educational materials.

Table 8 - Questions to assess effectiveness in HCP survey

Category of assessment	Question text [Answer options]	Criteria for 'effective assessment'
To assess if materials are being received and read	A2. Which of the following material have you received or had access to? Select all that apply 1. Summary of Product Characteristics (SMPC) 2. Fabrazyme Home Infusion Therapy: A guide for Healthcare professionals treating patients with Fabry disease 3. Fabrazyme Home Infusion Therapy: Manual for Patients with Fabry disease who receive home infusion of Fabrazyme 4. None of the above	Majority of HCPs selecting Code 2
	A3. Have you read the Fabrazyme (agalsidase beta) home infusion educational materials? 1. Yes 2. No	Majority of HCPs selecting Code 1
To assess evaluation of home infusion	B1. Do you use the educational materials to evaluate and select patients for home infusions? 1. Yes 2. No	Majority of HCPs selecting Code 1
	B2. Which of the following criteria must be fulfilled before a patient is deemed eligible for Fabrazyme (agalsidase beta) home infusion? Select all that apply 1. Patient must be medically stable 2. A comprehensive evaluation must be completed before deciding on transfer of therapy to home infusion 3. Patient must have received Fabrazyme infusions for several months in a controlled setting and previous infusions well tolerated 4. Don't know	Majority of HCPs selecting codes 1, 2 and 3
To assess level of training to patients/caregivers	B4. Do you use the Fabrazyme (agalsidase beta) home infusion educational materials when training the patient/caregiver on the home infusion process? 1. Yes 2. No	Majority of HCPs selecting Code 1

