	
A5. How often do you [or the patient] refer to the educational materials when the home infusions are being done?
 
1. At every infusion
 
2. Frequently
 
3. Rarely
 
4. Never
	Majority of patients selecting Code 1 or 2
To assess knowledge on preparation of infusion	
B3. Which of the following statements are true in relation to the preparation, administration and storage of Fabrazyme. Select all that apply
 
1. The vials must be removed from the refrigerator approximately 30 mins before preparation
 
2. The reconstituted mixture should be shaken up
 
3. The reconstituted solution must be clear and colourless before use
	Majority of patients selecting Code 1, 3 & 4

	
4. The tourniquet should be applied to identify a vein
 
5. The product can be stored at room temperature for 48 hours before use
 
6. None of the above are true
 
7. N/A I don't prepare the infusion on my own
	
To assess knowledge on actions taken in case of AE	
C5. What would you do if [you / the patient] developed a headache and a fever during the infusion?
 
1. Complete the infusion and then rest
 
2. Immediately stop the infusion
 
3. Contact the physician
 
4. Record details in the logbook
 
5. Don't Know
	Majority of patients selecting Code 2, 3 and 4
To assess implementation of logbook	
C1. Considering the Fabrazyme (agalsidase beta) home infusion, how often do you or the nurse who helps you with the infusion (if applicable) do the following actions?
 
[1. Always / 2. Regularly / 3. Rarely / 4. Never]
 
a. Fill out the infusion data in the logbook
 
b. Take the logbook to each appointment with the prescribing physician
	Majority of patients selecting codes 1 & 2 for both actions
	
C2. How often do you or the nurse who helps you with the infusion report changes about the infusion (dose or infusion rate) in [your / the patient's] logbook?
 
1. Always
 
2. Regularly
 
3. Rarely
 
4. Never
 
5. N/A There have been no changes
	Majority of patients selecting codes 1 or 2 (excluding those selecting code 5 from calculation)
	
C6. If [you / the patient] had a side effect, should you report the side effect in your log book?
 
1. Yes, always
 
2. Only if I think it's serious
 
3. No, it is not necessary
	Majority of patients selecting codes 1

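### Patient item B3 offers a not-applicable answer but does not remove it from the >70% calculation, although C2 in the same table removes its own

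*Protocol*

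**What the plan says.** Protocol section 8.7 gives one rule for all scored items: "a positive outcome is defined as at >70% of the survey participants providing a" correct response, with the items and their correct answers listed in Tables 8 and 9.

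In Table 9, B3 is the only scored patient item on preparation, administration and storage. It is a multiple-response question, and its criterion is "Majority of patients selecting Code 1, 3 & 4". Its last option, code 7, reads "N/A I don't prepare the infusion on my own". The criterion says nothing about how code 7 is handled.

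C2 is the only other scored patient item with a not-applicable option. Its criterion is "Majority of patients selecting codes 1 or 2 (excluding those selecting code 5 from calculation").

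Section 8.5.2 plans 18 patients or caregivers, and Table 7 gives precision on that base. Section 8.1.1 states that "Nurses play an important role in providing in person medical supervision and education to patients receiving Fabrazyme home infusion" in four of the five countries. Table 5 shows that the involvement of an infusion nurse or other trained professional is recorded.

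**The concern.** Table 9 sets the calculation base item by item. It removes the not-applicable answer for C2 and leaves it in for B3, where the general rule of "of the survey participants providing a" correct answer then applies. Someone whose infusion is prepared by a nurse or caregiver, or with help, and who truthfully ticks only code 7 does not meet the B3 criterion, just like someone who answers wrongly.

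The B3 percentage would then mix two things: what preparers know, and how many respondents prepare the infusion themselves. If enough respondents do not, B3 misses its threshold whatever the preparers know. Because B3 stands alone in its category, the report could show a shortfall in preparation knowledge that reflects only who prepares the infusion.

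**Working it through.** **Inputs.** n = 18 (section 8.5.2); threshold above 70% of survey participants (section 8.7); B3 and C2 criteria (Table 9). Two inputs are not in the protocol and are assumed: the share q choosing code 7 (range 0 to 40%), and the probability that a preparer selects codes 1, 3 and 4 (0.90). Code 7 is taken to be ticked alone.

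**The plan's own figures.** Half-width = 1.96 × √(p(1−p)/18) gives 18.5, 20.0, 21.2 and 22.6 points at p = 80, 75, 70 and 60%. These match Table 7, so its precision applies to a base of 18.

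**Threshold.** 12/18 = 66.7% and 13/18 = 72.2%, so 13 correct answers are needed.

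**Ceiling.** With k code-7-only answers left in, the best possible result is (18 − k)/18, and the rate needed among preparers is 13/(18 − k):

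| k | Best possible result | Needed among preparers |
|---|---|---|
| 0 | 100% | 13 of 18 (72.2%) |
| 4 | 77.8% | 13 of 14 (92.9%) |
| 5 | 72.2% | 13 of 13 (100%) |
| 6 | 66.7% | not attainable |

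The ceiling does not depend on the 90% assumption.

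**Chance of a positive result.** With code 7 left in, the number correct is binomial with 18 trials and probability 0.9(1 − q), and at least 13 are needed. With code 7 excluded, more than 70% of the 18 − k preparers must be correct, averaged over k ~ Bin(18, q).

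| q | Code 7 left in | Code 7 excluded |
|---|---|---|
| 0% | 0.99 | 0.99 |
| 10% | 0.89 | 0.99 |
| 20% | 0.61 | 0.98 |
| 30% | 0.29 | 0.97 |
| 40% | 0.09 | 0.96 |

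**If 'majority' meant only more than half.** Then 10 of 18 suffice. With code 7 left in, the chance is 0.96, 0.82 and 0.54 at q = 20, 30 and 40%, and a positive result becomes impossible from k = 9 (9/18 = 50%).

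**Precision after exclusion.** With 12 preparers, 1.96 × √(0.7 × 0.3/12) = 25.9 points at 70%, against 21.2 in Table 7.

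**The case against.** Five things can be said against the point.

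- **Nothing states that code 7 is scored as wrong.** The base is left to silence, and an analysis plan or the questionnaire (Appendix 2, not shown) could settle it. The first part stands, but Table 9 is where the protocol fixes the base for C2, and no text at hand routes non-preparers past B3. Leaving code 7 in is therefore the plain reading.
- **Respondents may tick several options, and code 7 is not declared exclusive.** A non-preparer who knows the manual could tick 1, 3, 4 and 7 and meet the criterion. This stands: the ceiling applies to respondents who tick code 7 alone.
- **The frequency of code 7 is unknown.** A reader might infer that it will be common because the four countries where nurses have an important role hold 422 of the 456 target patients (93%; Table 1: 140 + 190 + 65 + 27). The documents do not support that. The count covers all home-infusion patients there, and section 8.1.1 describes supervision and education, not preparation. The wording of C1 and C2, which mention a nurse who helps with the infusion, makes some code 7 answers plausible but gives no number. Code 7 may also cover preparation by or with a caregiver.
- **The effect is recoverable and B3 is not decisive.** A reader might infer that this one item could sink the evaluation. Section 8.7 is descriptive, reports counts and looks across several items, and section 11.2 asks for the results to be read together with safety and clinical outcomes. This stands and limits the severity.
- **Exclusion lets respondents opt out of a knowledge question and shrinks a small base.** This also stands, and the fix must deal with it.

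**Conclusion.** The point holds as an inconsistency within Table 9 that should be fixed; it does not threaten the study as a whole. Under the stated rule, respondents who tick only code 7 count against B3. At the planned 18, five of them leave no room for error among the rest, and six rule out a positive result. This ceiling rests only on n = 18, the >70% threshold and code 7 being ticked alone.

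How likely a misleading result is depends on the unknown code 7 share and on the assumed 90% correct among preparers. The loss is modest at 10% not applicable (0.89 against 0.99) and large from 20% (0.61 against 0.98). It is smaller if 'majority' is read as more than half, but section 8.7 favours the 70% threshold. The documents do not show that B3 will fail, only that it can fail for a reason unrelated to knowledge.

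**What to change.** - Add to the B3 criterion in Table 9 the exclusion that C2 already has ("excluding those selecting code 5 from calculation"), with code 7 in place of code 5.
- Make code 7 an exclusive answer in the survey script, so that it cannot be combined with codes 1 to 6.
- Report the number choosing code 7, the resulting base, and the precision on that base instead of the Table 7 figure.
- Cross-tabulate code 7 with the nurse-involvement item listed in Table 5, so that use of code 7 to avoid the question by people who do prepare infusions becomes visible.

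The cost is one line in Table 9, one scripting rule and one extra table, with no new data. The downside is a base below 18 for B3 and a wider interval. Making the change before results are seen avoids choosing the denominator afterwards.

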8.5.2 Patient sample size

A total sample size of 18 Patients and/or Caregivers will be recruited across key countries previously described in ‘8.2 setting’. Given the rarity of the patient universe we are targeting, the patient sample numbers included are driven primarily by feasibility.

Sample size feasibility the calculations were based on several factors/assumptions:

- Total number of eligible patients is assumed to be 456 based on France, UK, Italy, Finland and Norway data in Table 2
- The patient recruitment approach will be via HCP referrals
 - All HCPs contacted are asked to pass on details of the survey to eligible patients, however there is a higher likelihood that HCPs who participate will encourage their patients to also participate. Thus, most conservative patient reach estimate would be limited to the patients treated by these 34 HCPs (~40%) or 180 patients.
- Assumed that despite best efforts the patient response rate will be low based on:
 - Reliance on HCPs informing all Fabrazyme patients/caregivers of the study
 - Reliance of patients/caregivers in being proactive in responding to the invitation letters

Table 7 describes the level of precision for a sample of 34 for a selection of response levels to a particular question.

Table 7 - Precision estimates for the target patient/caregiver sample size (n=18) for 60, 70, 80% correct response levels

Correct response percentage	Lower limit	Upper limit	Precision (+/-)
80%	61.5%	98.5%	18.5%
75%	55.0%	95.0%	20.0%
70%	48.8%	91.2%	21.2%
60%	37.4%	82.6%	22.6%

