	B5. How frequently do you cover each of the following areas when training the patient/caregiver on Fabrazyme home infusion? [1. Always / 2. Regularly / 3. Rarely / 4. Never] a. Importance of adhering to the pre-defined infusion schedule (dose and infusion rate) b. Method of preparation, reconstitution and administration c. Instructions for handling Adverse Events (AEs) and Infusion Associated Reactions (IARs) d. Completing the logbook	Majority of HCPs selecting codes 1 & 2 for each area
To assess knowledge on actions taken in case of IAR and AE	B6. In the event of an infusion associated reaction (IAR) what are the appropriate steps that should be taken? Select all that apply 1. Infusion is immediately discontinued	Majority of HCPs selecting codes 1 & 3

	
2. Infusion is completed and IAR recorded in the logbook
 
3. Patient/Infusion nurse to call the treating physician immediately
 
4. Don't Know
	
To assess implementation of logbook	
C1. How often do you clearly state the Fabrazyme (agalsidase beta) home infusion administration details in the logbook of your Fabry patients? [1. Always / 2. Regularly / 3. Rarely / 4. Never]
	Majority of HCPs selecting codes 1 & 2
	
C2. How often do you review your patients' logbooks? [1. Always / 2. Regularly / 3. Rarely / 4. Never]
	Majority of HCPs selecting codes 1 & 2
	
C4. Considering the logbook, how often do you do each of the following: [1. Always / 2. Regularly / 3. Rarely / 4. Never]
 
a. Document changes to the infusion schedule
 
b. Check the infusion rate
 
c. Check the dose administered
 
d. Discuss logbook with patient/caregiver
	Majority of HCPs selecting codes 1 & 2 for each element

Table 9 - Questions to assess effectiveness in patients/caregivers survey

Category of assessment	Question text [Answer options]	Criteria for 'effective assessment'
To assess if materials are being received read and referred to	
A2. Have you [or the person you care for] received any of the following? Select all that apply
 
1. Package leaflet for Fabrazyme
 
2. Fabrazyme Home Infusion Therapy: Manual for Patients with Fabry disease who receive home infusion of Fabrazyme
 
3. None of the above
	Majority of patients selecting Code 2
	
A3. Have you read the Fabrazyme (agalsidase beta) home infusion educational materials?
 
1. Yes
 
2. No
	Majority of patients selecting Code 1

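### Patient item B3 keeps its not-applicable answers in the denominator, while C2 in the same table removes them, so B3 mixes who prepares the infusion with who knows the steps

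*Protocol*

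**What the plan says.** Protocol section 8.7 fixes a general rule: "a positive outcome is defined as at >70% of the survey participants providing a" correct response. Tables 8 and 9 then give the criterion for each item.

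For patient item B3 in Table 9, the only item in the category on preparation knowledge, the criterion is "Majority of patients selecting Code 1, 3 & 4". The item is multiple-response. Its last option, code 7, is a not-applicable answer for a respondent who does not "prepare the infusion on my own". The criterion says nothing about how code 7 is handled.

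Item C2, further down the same table, also has a not-applicable option, for patients whose infusion has not changed. Its criterion carries an explicit instruction: "excluding those selecting code 5 from calculation".

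Section 8.5.2 sets the size: "A total sample size of 18 Patients and/or Caregivers will be recruited". Section 8.1.1 says of the UK, France, Italy and Finland that "Nurses play an important role in providing in person medical supervision and education to patients receiving Fabrazyme home infusion".

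**The concern.** Two items in one table have a not-applicable code, and only one of them drops it from the calculation. Since the table states an exclusion where one is wanted, a literal reading of B3 leaves code-7 respondents in the denominator. They have not given the scored answer, so they count against the item.

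B3 then depends on two things at once: how many respondents prepare the infusion themselves, and how many of those know the steps. A low percentage could come from either. With 18 respondents, a few code-7 answers are enough to move the item across the 70% line. This is a fixed decision criterion in the protocol, and an analysis plan that added the exclusion would be departing from it.

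**Working it through.** **Inputs.** n = 18 (section 8.5.2). Pass mark above 70% of participants (section 8.7). Correct answer on B3 is codes 1, 3 and 4 (Table 9). The number on code 7, written k, and its expected share, written q, are not in the protocol and are varied below. Knowledge among preparers, written p, is assumed.

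**The protocol's own figure.** Table 7 is reproduced by 1.96 × √(P(1−P)/18), where P is the percentage correct. For 80%, 75%, 70% and 60% this gives half-widths of 18.5, 20.0, 21.2 and 22.6 points, as printed. The planned precision therefore uses all 18 as denominator.

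**Count needed.** 12/18 = 66.7% fails and 13/18 = 72.2% passes, so 13 correct answers are required.

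**Ceiling with code 7 kept in.** If code 7 is never combined with codes 1, 3 and 4, the highest possible result is (18 − k)/18, and the preparers must score 13/(18 − k). With code 7 excluded, the count needed is the smallest r with r/(18 − k) above 70%.

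| k | Highest possible | Needed among preparers | Needed if excluded |
|---|---|---|---|
| 0 | 100% | 13 of 18 (72.2%) | 13 of 18 |
| 3 | 83.3% | 13 of 15 (86.7%) | 11 of 15 |
| 4 | 77.8% | 13 of 14 (92.9%) | 10 of 14 |
| 5 | 72.2% | 13 of 13 (100%) | 10 of 13 |
| 6 | 66.7% | not reachable | 9 of 12 |

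Smaller numbers on code 7 already matter. At k = 3 and p = 0.80, the chance of passing is 0.40 with code 7 kept in (at least 13 of 15) and 0.84 with it excluded (at least 11 of 15).

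**Chance of passing when k is random.** As written, each respondent is correct with probability (1 − q)p, so the chance is P(X ≥ 13) for X binomial with n = 18. With exclusion, the chance of reaching the required count among 18 − k preparers is averaged over k, binomial(18, q). With p = 0.90:

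| q | (1 − q)p | Passes as written | Passes with code 7 excluded |
|---|---|---|---|
| 10% | 0.81 | 0.89 | 0.99 |
| 20% | 0.72 | 0.61 | 0.98 |
| 30% | 0.63 | 0.29 | 0.97 |
| 40% | 0.54 | 0.09 | 0.96 |

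The chance that k is 6 or more, so that the item cannot pass at all, is 0.006, 0.13 and 0.47 at q = 10%, 20% and 30%.

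**The case against.** **The share on code 7 is unknown.** A reader might infer from section 8.1.1 that code 7 will be common. That section describes nurses supervising and educating; it does not say that they prepare the infusion. Table 9 refers to nurse help only where applicable, and item B5 of Table 8 has HCPs training patients and caregivers in preparation. This objection stands, so the result is given over a range. At 10% on code 7 the loss is modest.

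**Code 7 may not be exclusive.** Respondents may tick several options on B3, and someone who does not prepare can still judge which statements are true. The protocol does not say that code 7 blocks the others; the logic checks are left to the data collection materials, which are not shown. The ceiling holds only if code 7 is not combined with codes 1, 3 and 4. This stands as a stated assumption.

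**Table 9 says majority.** Read as more than 50%, 12/18 would pass and the item would become unreachable at k = 9 (9/18 = 50.0%) instead of 6. Section 8.7 fixes more than 70% for this assessment, so that figure is used.

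**One failed item does not condemn the materials.** A reader might infer a false negative verdict overall. Section 8.7 speaks of a positive outcome across the key questions and makes no single item decisive. The analysis is descriptive, with counts by category, so the code-7 count should be visible. Section 11.2 asks for interpretation alongside safety and clinical outcomes. This stands and limits the consequence to B3.

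**HCP item C4a.** A reader might see the same fault in "Document changes to the infusion schedule", which has no option for no changes. The documents do not support that. An HCP who records every change can answer Always, and the item covers a caseload, on average 456/83 ≈ 5.5 patients per prescriber from Table 1, where C2 concerns one patient. An added code there would be a questionnaire preference.

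None of this explains why B3 and C2 treat their not-applicable codes differently.

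**Conclusion.** The inconsistency is real and should be fixed. Under the stated rule, respondents to whom B3 does not apply count as incorrect, and the item can fail although nearly all preparers know the steps. If 90% of preparers answer correctly, the loss in the chance of passing at n = 18 runs from about 0.10 with 10% on code 7 (0.99 against 0.89) to about 0.87 with 40% (0.96 against 0.09). With six or more on code 7 the item cannot pass.

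The size rests on three assumptions: the code-7 share, the 90% knowledge level, and code 7 not being combined with the scored codes. The mismatch between B3 and C2 rests on none of them. The consequence is a possible false negative on item B3 only.

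**What to change.** In Table 9, add to the B3 criterion: (excluding those selecting code 7 from calculation), matching C2. Program code 7 as an exclusive answer in the online questionnaire. In the report, give the number excluded and the resulting denominator next to the B3 percentage. No change to C4a is needed.

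The cost is one line in the table and one logic check, best made before fieldwork. The price is precision. With six excluded, the half-width at 80% correct grows from 18.5 points (n = 18) to 1.96 × √(0.8 × 0.2/12) = 22.6 points (n = 12), and the result then describes only respondents who prepare the infusion.

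### Patient item C5 (Table 9) is scored on three codes together, but its printed text does not tell respondents that they may select more than one

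*Protocol*

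**What the plan says.** Protocol section 8.7 sets one pass rule for all scored questions: "a positive outcome is defined as at >70% of the survey participants providing a ‘correct’ response". Table 9 then gives the text and criterion of each scored patient/caregiver question.

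- **C5** is the only question in the Table 9 category on knowledge of what to do in case of an adverse event. It reads "C5. What would you do if [you / the patient] developed a headache and a fever during the infusion", followed by five answer codes. No instruction on the number of answers is printed. The criterion is "Majority of patients selecting Code 2, 3 and 4".
- **B3**, in the same table, also needs three codes and prints the instruction: "B3. Which of the following statements are true in relation to the preparation, administration and storage of Fabrazyme. Select all that apply".
- **B6** in Table 8, the HCP question on the same topic, needs two codes and prints it as well: "what are the appropriate steps that should be taken? Select all that apply".
- **C1** in Table 9 names a second possible actor: "how often do you or the nurse who helps you with the infusion (if applicable) do the following actions". C2 uses similar wording. C5 asks only what the respondent would do; its bracket changes who has the symptoms, not who acts.

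Section 7 lists actions in case of an adverse event among the content areas of the primary objective. Section 8.5.2 sets the patient/caregiver sample at 18.

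**The concern.** The question text and the scoring key of C5 do not match. The key assumes a multiple-response item, while the text reads like a request for one best answer. Table 9 otherwise follows a consistent convention, so the omission on C5 looks like a slip and not a choice.

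A respondent who knows all three keyed actions but ticks only the one that seems most important is counted the same as one who does not know what to do. The item would then partly measure how the question was read. With 18 respondents and a fixed cut point, a handful of such answers decides whether this content area is reported as a positive outcome among patients.

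**Working it through.** **1. Convention check across Tables 8 and 9.** These are the scored list items that can take more than one code:

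| Item | Codes in the criterion | Multi-select instruction printed |
|---|---|---|
| HCP A2 | 2 | yes |
| HCP B2 | 1, 2, 3 | yes |
| HCP B6 | 1, 3 | yes |
| Patient A2 | 2 | yes |
| Patient B3 | 1, 3, 4 | yes |
| Patient C5 | 2, 3, 4 | **no** |

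C5 is the only exception.

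**2. The plan's own figures at n=18.** No stated figure depends on C5, but Table 7 confirms the basis. The 95% Wald half-width is 1.96 × √(p(1−p)/n). For p = 0.70 and n = 18 it is 1.96 × √(0.21/18) = 1.96 × 0.1080 = 0.212, giving 48.8% to 91.2% as printed. The other three rows of Table 7 also reproduce, and so does Table 6 with n = 34.

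**3. The pass count.** I read the majority named in the Table 9 criteria as the >70% cut point of section 8.7. Then 12/18 = 66.7% fails and 13/18 = 72.2% passes. Six respondents scored incorrect, for whatever reason, fail the item.

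**4. Effect of incomplete answers.** Let k be the true share who know the keyed actions, and m the share of those who answer incompletely because of the wording. The expected correct rate is p = k(1−m), and P(pass) = P(X ≥ 13) with X ~ Binomial(18, p). The protocol gives neither k nor m; both are assumptions, shown over a range.

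| m | p at k=80% | P(pass) | p at k=90% | P(pass) | p at k=100% | P(pass) |
|---|---|---|---|---|---|---|
| 0% | 0.80 | 0.867 | 0.90 | 0.994 | 1.00 | 1.000 |
| 10% | 0.72 | 0.609 | 0.81 | 0.890 | 0.90 | 0.994 |
| 20% | 0.64 | 0.322 | 0.72 | 0.609 | 0.80 | 0.867 |
| 30% | 0.56 | 0.124 | 0.63 | 0.291 | 0.70 | 0.534 |
| 40% | 0.48 | 0.033 | 0.54 | 0.093 | 0.60 | 0.209 |

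The expected rate falls to 70% when m = 1 − 0.70/k, which is 12.5%, 22.2% and 30.0% for k = 80%, 90% and 100%. The calculation assumes 18 completed surveys, independent respondents, and no correct answers from those who lack the knowledge. The m = 0 row is the ideal result of a clear instruction.

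**The case against.** The strongest reply is that Table 9 is not the fielded instrument. The survey is Appendix 2, which is listed but was not available for this review. A three-code key presupposes multiple response. Section 8.8.1 also promises clear instructions at each question, checks of programmed logic before fieldwork, a patient/caregiver pilot with telephone debrief, and a soft launch with data review. A script in which nobody could be correct should be caught there.

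This stands in part. It makes single-choice scripting unlikely, so a reader should not infer a 0% correct rate; that follows only under a script the documents do not show. It does not remove the mismatch in the protocol's own table. None of those checks is described as comparing an item with its scoring key, and one ticked box on a multi-select screen breaks no logic rule.

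It could also be said that the joint reading of the key is not certain, because the frequency items (for example C1) join alternative codes with an ampersand. But those are scales with one answer per row. C5 lists separate actions, and B2, B3 and B6 use the same form of key with the multi-select instruction.

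A reader might go further and infer that patients whose nurse runs the infusion are scored as lacking knowledge. The documents do not support that. C5 is hypothetical, and a nurse-assisted patient can select codes 2, 3 and 4 like anyone else. C1 and C2 name the nurse because they ask how often shared tasks are done. Section 8.1.1 does say "Nurses play an important role in providing in person medical supervision and education to patients receiving Fabrazyme home infusion" and names the UK, France, Italy and Finland, which hold 140 + 190 + 65 + 27 = 422 of the 456 patients (92.5%) in Table 1. That is where patients live, not the share with a nurse running the infusion, which the protocol does not give. What remains is a smaller risk that some answer only for their own role. B3 gives such respondents a way out, "N/A I don't prepare the infusion on my own"; C5 has none.

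**Conclusion.** The point holds as an inconsistency between the printed text of C5 and its scoring rule. If C5 is fielded as printed, respondents who know the keyed actions but give one answer count as incorrect on the only item in its category, and six such answers among 18 are enough to fail it. The size rests on an assumed rate of incomplete answering: at 90% true knowledge, a rate of 20% lowers the chance of passing from 0.99 to 0.61, and the assumed range of 0 to 40% spans 0.99 to 0.09.

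A reader might infer a false negative conclusion about the patient manual as a whole. That is not shown. Section 8.7 looks across several questions, C6 also touches on side effects (as a logbook item), and section 11.2 wants the results read together with safety and clinical outcomes. The nurse wording is a secondary matter: having a nurse does not by itself make a patient score as incorrect.

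**What to change.** - Print the multi-select instruction on C5 in Table 9 and in the patient survey, in the form used for B3 and B6, and script the item as multiple response. Leave the keyed actions unchanged.
- Report the frequency of each C5 code beside the all-three-codes result, so that incomplete answers can be told apart from wrong ones.
- As a secondary step, align the stem with C1 and C2 so that it covers the respondent or the nurse who helps. This reduces the risk of answers given only for the respondent's own role.

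The cost is a phrase in one question and its translations, one script setting before fieldwork, and a few descriptive table rows. Sample size and pass rule are unaffected.
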